7.0 Treatment Delays/Treatment Modifications

In order to maintain dose-intensity and cumulative dose-delivery on this study, reasonable efforts will be made to minimize dose reduction and treatment delays as specified. Any patient whose treatment is delayed must be evaluated on a weekly basis until adequate hematologic and non-hematologic parameters have been met. No dose escalation is planned for this study.

7.1 General Guidelines for Hematologic Toxicity

- 7.1.1 Treatment decisions will be based on the absolute neutrophil count (ANC) rather than the total white cell count (WBC).
- 7.1.2 Lower Limits for ANC and Platelet Count: ANC must be ≥ 1500 and platelets $\geq 75,000$ to proceed with HIPEC with carboplatin 800 mg/m².
- 7.1.3 Use of Hematopoietic Cytokines and Protective Agents

The use of hematopoietic cytokines and protective reagents are restricted as noted:

A Phase II Trial Evaluating Quality of Life After HIPEC in Patients with Stage IIIC and IV Ovarian, Fallopian Tube or Primary Peritoneal Carcinoma
Wake Forest Baptist Comprehensive Cancer Center (WFBCCC)
CCCWU 83216

7.1.3.1 In general, patients will NOT receive prophylactic filgrastim (G-CSF), PEG-filgrastim (Neulasta), or sargramostim (GM-CSF) unless they experience treatment delays or neutropenic delays or have missed or omitted doses, and should follow treatment modifications as specified for the following cycle (see Table A). However, patients may receive growth factors for management of neutropenic complications (e.g. neutropenic fever) in accordance with clinical treatment guidelines. G-CSF prophylactic treatment is recommended in subsequent cycles according to the tables A and B. Treating physicians are allowed some flexibility for treatment for severe neutropenia in the elderly for documented safety concerns.

7.1.3.2 Patients will NOT receive prophylactic thrombopoietic agents.

7.1.3.3 Patients may receive iron supplements and/or transfusions as clinically indicated for management of anemia. Treating physicians should be aware of the recent changes in prescribing information for the erythropoiesis stimulating agents (including Aranesp, EpoGen and Procrit) which note that there is a potential risk of shortening the time to tumor progression or disease-free survival, and that these agents are administered only to avoid red blood cell transfusions. They are not indicated in patients being treated with curative intent. They do not alleviate fatigue or increase energy. They should not be used in patients with uncontrolled hypertension. They can cause an increased incidence of thrombotic events in cancer patients on chemotherapy. The updated package inserts should be consulted.
<http://www.fda.gov/Medwatch/safety/2007/safety07.htm>

7.2 **Unanticipated Major Surgical Procedures** – (Report all surgery on the Surgery Form Appendix D) For any unanticipated (emergent/urgent) major surgical procedure performed for reasons other than disease progression treatment should be held > 28 days postoperatively. Treatment delay is not required for minor procedures including a) the removal or insertion of a central venous catheter, nephrostomy tube, or ureteral stent or b) thoracentesis or paracentesis for symptom relief in the absence of disease progression.

7.3 Cardiac Toxicity

Symptomatic bradycardia is not an indication for routine monitoring or removal from study. Any arrhythmia or cardiac ischemia event should be discussed with Study Chair, and patient should be removed from study therapy if this is deemed necessary.

8.0 Measurement of Effect

8.1 Definitions

Evaluable for toxicity. All patients will be evaluable for toxicity after the first administration of chemotherapy.

Evaluable for objective response. Only those patients who have measurable disease present at baseline, have received one cycle of therapy, and have had their disease re-evaluated will

A Phase II Trial Evaluating Quality of Life After HIPEC in Patients with Stage IIIC and IV Ovarian, Fallopian Tube or Primary Peritoneal Carcinoma
Wake Forest Baptist Comprehensive Cancer Center (WFBCCC)
CCCWFU 83216

be considered evaluable for response. These patients will have their response classified according to the definitions stated below.

Hematologic toxicities will be recorded in accordance with the Common Terminology Criteria for Adverse Events (CTCAE) Version 5.0.

Response and progression will be evaluated in this study using the new international criteria proposed by the Response Evaluation Criteria in Solid Tumors (RECIST) Committee [JNCI 92(3):205-216, 2000]. Changes in only the largest diameter (unidimensional measurement) of the tumor lesions are used in the RECIST criteria.

Measurable disease. Measurable lesions are defined as those that can be accurately measured in at least one dimension (longest diameter to be recorded) as ≥ 20 mm with conventional techniques (CT, MRI, x-ray) or as ≥ 10 mm with spiral CT scan. All tumor measurements must be recorded in millimeters (or decimal fractions of centimeters).

Non-measurable disease. All other lesions (or sites of disease), including small lesions (longest diameter <20 mm with conventional techniques or <10 mm using spiral CT scan), are considered non-measurable disease. Bone lesions, leptomeningeal disease, ascites, pleural/pericardial effusions, lymphangitis cutis/pulmonis, inflammatory breast disease, abdominal masses (not followed by CT or MRI), and cystic lesions are all non-measurable.

Target lesions. All measurable lesions up to a maximum of 5 lesions per organ and 10 lesions in total, representative of all involved organs, should be identified as target lesions and recorded and measured at baseline. Target lesions should be selected on the basis of their size (lesions with the longest diameter) and their suitability for accurate repeated measurements (either by imaging techniques or clinically). A sum of the longest diameter (LD) for all target lesions will be calculated and reported as the baseline sum LD. The baseline sum LD will be used as reference by which to characterize the objective tumor response.

Non-target lesions. All other lesions (or sites of disease) including any measurable lesions over and above the 10 target lesions should be identified as non-target lesions and should also be recorded at baseline. Measurements of these lesions are not required, but the presence or absence of each should be noted throughout follow-up.

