6.2.1.2 HIPEC

Tumor Debulking and Establishment of Peritoneal Perfusion Circuit

The HIPEC will be preceded by a complete cytoreduction to maximize its therapeutic benefit. The goal of cytoreduction will be resection of all gross tumor. A generous midline incision will be utilized for all explorations. Resection of the peritoneum by stripping it off the abdominal wall combined with multi-visceral resections (such as splenectomy, large and small bowel resection, hysterectomy, etc.) will be utilized for maximal tumor debulking¹⁹.

Patients will be cooled to a core temperature of about 34 to 35° C by passive measures (i.e., not warming airway gases or intravenous solutions) during cytoreduction. After the completion of cytoreductive surgery, peritoneal perfusion catheters will be placed percutaneously. Two inflow catheters (22Fr) will be directed beneath the left and right hemidiaphragms. One or two outflow catheters (32Fr) will be placed in the pelvis. Intraperitoneal catheters will be placed as per institutional standard practice. Temperature probes will then be placed on the inflow and outflow catheters. The abdominal skin incision will be temporarily closed with a running suture to prevent leakage of peritoneal perfusate. A perfusion circuit will be established with 3 L of crystalloid perfusate solution, such as sodium chloride, Lactated Ringers or Plasmalyte. If a perfusion circuit cannot be established with 3 liters a 4th liter is acceptable, but under no circumstances should the volume of perfusate be greater than 4 liters. Flow rates should be at least one liter per minute. The pelvic catheters will drain to a reservoir containing a coarse filter for debris and to reduce foaming. The heated chemotherapy solution will be added and circulated through the institution's standard perfusion equipment. The temperature of the fluid in the patient-return and patient-directed tubing will be monitored using stainless steel couplers with temperature probe connectors and needle probes at the tips of one inflow and one outflow cannula. The abdomen will be gently massaged throughout the perfusion to improve drug distribution to all peritoneal surfaces. Constant temperature monitoring will be done at all temperature probes. A perfusion record will be completed during HIPEC (see Appendix E). Following the perfusion, the peritoneum will be washed out with 3 liters of the crystalloid perfusate.

HIPEC Chemotherapy Administration

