6.5 Duration of Follow Up

Tumor assessment for all lesions will be performed while patients are in the protocol follow-up phase of this study at 3, 6, and 12 months. Patients who discontinue the trial without documented tumor progression should be evaluated for extent of disease at the time of trial discontinuation.

Patients will be followed for 30 days after the HIPEC intervention is administered for adverse events monitoring.

A Phase II Trial Evaluating Quality of Life After HIPEC in Patients with Stage IIIC and IV Ovarian, Fallopian Tube or Primary Peritoneal Carcinoma
Wake Forest Baptist Comprehensive Cancer Center (WFBCCC)
CCCWU 83216

Patients will be followed for a minimum of 30 days after removal from study or until death, whichever occurs first. Patients removed from study for unacceptable adverse events will be followed until resolution or stabilization of the adverse event.

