8.5 Methods for Evaluation of Measurable Disease

All measurements should be taken and recorded in metric notation using a ruler or calipers. All baseline evaluations should be performed within 90 days of registration prior to surgery.

The same method of assessment and the same technique should be used to characterize each identified and reported lesion at baseline and during follow-up. Imaging-based evaluation is preferred to evaluation by clinical examination when both methods have been used to assess the antitumor effect of a treatment.

Clinical lesions: Clinical lesions will only be considered measurable when they are superficial (e.g., palpable abdominal masses). In the case of palpable lesions, documentation by color photography, including a ruler to estimate the size of the lesion, is recommended.

Chest X-ray: Lesions on chest x-ray are acceptable as measurable lesions when they are clearly defined and surrounded by aerated lung. However, CT is preferable.

Conventional CT and/or MRI: These techniques should be performed with cuts of 5 mm or less in slice thickness contiguously. Spiral CT should be performed using a 2.5 mm contiguous reconstruction algorithm. This applies to tumors of the chest, abdomen, and pelvis.

Tumor markers: Tumor markers alone cannot be used to assess response. If markers are initially above the upper normal limit, they must normalize for a patient to be considered in complete clinical response.

Cytology & Histology: These techniques can be used to differentiate between partial responses (PR) and complete responses (CR) in rare cases (e.g., where known residual benign tumors can remain).

The cytological confirmation of the neoplastic origin of any effusion that appears or worsens during treatment when the measurable tumor has met criteria for response or stable disease is

A Phase II Trial Evaluating Quality of Life After HIPEC in Patients with Stage IIIC and IV Ovarian, Fallopian Tube or Primary Peritoneal Carcinoma
 Wake Forest Baptist Comprehensive Cancer Center (WFBCCC)
 CCCWFU 83216

mandatory to differentiate between response or stable disease (an effusion may be a side effect of the treatment) and progressive disease.

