The best overall response is the best response recorded from the start of the treatment until disease progression/recurrence (taking as reference for progressive disease the smallest measurements recorded since the treatment started). The patient's best response assignment will depend on the achievement of both measurement and confirmation criteria.

Target Lesions	Non-Target Lesions	New Lesions	Overall Response	Best Response for this Category Also Requires:
CR	CR	No	CR	>4 wks. confirmation
CR	Non-CR/Non-PD	No	PR	>4 wks. confirmation
PR	Non-PD	No	PR	
SD	Non-PD	No	SD	Documented at least once >4 wks. from baseline
PD	Any	Yes or No	PD	no prior SD, PR or CR
Any	PD*	Yes or No	PD	
Any	Any	Yes	PD	

* In exceptional circumstances, unequivocal progression in non-target lesions may be accepted as disease progression.

Note: Patients with a global deterioration of health status requiring discontinuation of treatment without objective evidence of disease progression at that time should be reported as "*symptomatic deterioration*". Every effort should be made to document the objective progression even after discontinuation of treatment.

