Appendix G - MEASUREMENT FORM RECIST

Target Lesions										
TARGET Lesions	Lesion	Site	Imaging (ie, CT, MRI)	Baseline Date: (Se, Im)	Cycle____ Date: (Se, Im)					
	01				mm	mm	mm	mm	mm	mm
	02				mm	mm	mm	mm	mm	mm
	03				mm	mm	mm	mm	mm	mm
	04				mm	mm	mm	mm	mm	mm
	05				mm	mm	mm	mm	mm	mm
	Sum of Diameters				mm	mm	mm	mm	mm	mm
% Change (% Δ) from Baseline or Nadir* & absolute value (AbV)				NA	% Δ					
				NA	AbV					
Target Lesion Response				N/A						
Non-Target Lesions										
NON-TARGET Lesions	Lesion	Site	Imaging	Baseline	Cycle____	Cycle____	Cycle____	Cycle____	Cycle____	
	01									
	02									
	03									
	04									
	05									
Non-Target Lesion Response				N/A						
New Lesions										
New	1			N/A						
	2			N/A						
	3			N/A						
Overall Tumor Response					Cycle____	Cycle____	Cycle____	Cycle____	Cycle____	
Radiologist Signature:										
Treating Physician Signature:										
PI Signature:										

Completed By: _____ Signature of Principal Investigator* _____

Date Completed: ____ / ____ / ____ Date Completed ____ / ____ / ____

(*Signature needed for Assignment of Final Response at time of progression or End of Study)

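### Response is measured against a pre-operative baseline, so target lesions removed at surgery can be counted as RECIST response; sections 5.2.5 and 8.1 also point to different RECIST criteria

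*Combined protocol and SAP*

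**What the plan says.** All references are to the combined protocol and SAP.

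- **Reference.** Section 8.1 (target lesions): "The baseline sum LD will be used as reference by which to characterize the objective tumor response".
- **Timing of baseline.** Section 8.5: "All baseline evaluations should be performed within 90 days of registration prior to surgery". The schedule in 6.1 has a single CT before follow-up, at the pre-study visit, within 28 days before registration. The 28-day and 90-day windows differ, but both fall before surgery.
- **Surgery.** Section 6.2.1.2: "The goal of cytoreduction will be resection of all gross tumor".
- **Follow-up.** Section 6.5 says that tumour assessment "will be performed while patients are in the protocol follow-up phase of this study at 3, 6, and 12 months". Section 6.1 schedules no CT on the day of surgery or at 6 weeks.
- **Who is evaluable.** Section 8.1: "Only those patients who have measurable disease present at baseline, have received one cycle of therapy, and have had their disease re-evaluated". It does not ask for measurable disease after surgery.
- **Best response.** Section 8.5: "The best overall response is the best response recorded from the start of the treatment until disease progression/recurrence".
- **Analysis.** Section 13.2.5 gives counts and percentages at each time point. It does not mention excised lesions or resection status, although the Surgery Form (Appendix D) records resection status as R0 to R2c.
- **RECIST version.** Outcome 5.2.5 specifies v1.1. Section 8.1 applies the committee's criteria published in 2000, with at most 10 target lesions. Section 13.2.5 gives no version.

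**The concern.** A RECIST response rate is normally read as tumour shrinkage under treatment. Here the largest expected change in measurable tumour between the reference scan and the first follow-up scan is its surgical removal. If a removed lesion is scored as a lesion that has disappeared, the patient can be classed as a responder whatever the HIPEC did. A reader of the published rate could not tell removal from shrinkage, and the figure would partly repeat what the Surgery Form already records.

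The text does not settle the scoring. Section 8.1 promises that "These patients will have their response classified according to the definitions stated below", but the supplied text contains no target-lesion definitions of complete response, partial response, stable disease or progression. Citing two sets of RECIST criteria also leaves open which rules and which lesion limit were applied.

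**Working it through.** The plan states no response-rate figure, so there is none to reproduce. Its only design figure, the minimal detectable FACT-O difference in 13.3, is not an input here. The check is a reading of the sections in sequence, followed by one piece of arithmetic.

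**Step 1: order of events.** Pre-study CT (6.1, 8.5), then cytoreduction and HIPEC (6.2.1.2), then CT at 3, 6 and 12 months (6.1, 6.5). The reference is the first of these. No scheduled scan falls between surgery and 3 months, so the baseline cannot be read as a post-operative scan.

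**Step 2: effect of excision on the sum of diameters.** Let f be the fraction of the baseline sum that is excised, with the remaining lesions unchanged. If excised lesions contribute zero, the change in the sum is −100 × f per cent: −30% for f = 0.3, −80% for f = 0.8 and −100% for f = 1. Surgery alone produces these changes.

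**Step 3: what the response table in 8.5 then gives.** Suppose the target lesions are read as a complete response and there is no new lesion. Non-target complete response gives overall CR. Non-target disease that is neither complete response nor progression gives overall PR. If the target lesions are read as a partial response without non-target progression, the result is PR. A new lesion or non-target progression gives PD. So excision can lead to CR or PR.

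**Step 4: limits printed in 8.5.** CR needs confirmation after more than 4 weeks; the same entry stands against the PR row reached through target CR. An excised lesion stays absent, and the 3- and 6-month visits are about 13 weeks apart, or at least 13 − 2 − 2 = 9 weeks with the ±2-week windows. A later scan without progression can therefore meet the requirement. CR also requires markers that were initially raised to return to normal. That rule does not restrict PR.

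**Step 5: illustration of size.** Inputs:

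- E = 50 patients (13.3), all assumed evaluable and all kept in the 8.1 denominator.
- k = patients with every target lesion excised, no new lesion and no non-target progression (assumed).
- s = responders among the rest (any value).

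If excised lesions count as response, the rate is (k + s)/E. If they do not count, it is s/E. The difference is k/E, whatever s is:

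| k | k/50 | Difference (percentage points) |
|---|---|---|
| 5 | 5/50 | 10 |
| 25 | 25/50 | 50 |
| 45 | 45/50 | 90 |

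The documents give neither a resection rate nor the number of patients with measurable disease, so no value of k is more supported than another.

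**The case against.** The strongest reply is that objective 2.2.5 and outcome 5.2.5 describe response after the whole sequence of neoadjuvant chemotherapy, cytoreduction and HIPEC, so surgery is part of what is evaluated. On that view the plan never promises to separate removal from shrinkage, and there is no comparator, test or decision rule to be biased. This has weight: the documents do not demonstrate a bias. What remains is that a rate labelled RECIST response would partly measure completeness of resection, without the plan saying so.

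Second, the target-lesion definitions may have been lost when the text was extracted, since the numbering in section 8 has gaps and runs out of order. That is fair, and their absence is not held against the plan. The pre-operative reference and the two RECIST sources are printed and stand regardless.

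Third, Appendix G requires radiologist, treating physician and principal investigator signatures. These are a safeguard on assessment, but they do not supply a rule for excised lesions.

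A reader might also infer three stronger points that the documents do not support:

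- That patients with excised lesions leave the denominator. Under 8.1, a patient with baseline measurable disease who is treated and rescanned stays evaluable.
- That the five target rows on Appendix G contradict the 10-lesion limit. The form prints no maximum, so this is weak evidence.
- That 8.1 names a competing version number. It identifies its criteria by the 2000 publication and the lesion limit.

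**Conclusion.** The point holds. Followed as written, the reference rule in 8.1 lets surgical removal of target lesions count as CR or PR in the 13.2.5 rate, with CR limited by the confirmation and marker rules. The RECIST source in 5.2.5 does not agree with that in 8.1.

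The size cannot be estimated from the documents. The 10, 50 and 90 points are an illustration that rests on all 50 patients being evaluable and on assumed values of k. Measurable disease is not an entry criterion in 3.1, so the evaluable number may well be below 50. It would be tempting to say that the rate will be inflated by some such amount. The documents show only that it can be, because they leave the scoring open.

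The endpoint is secondary and descriptive. The FACT-O primary analysis and sample size are unaffected, and no effect on progression-free survival is claimed. The change should be made because it is cheap and a descriptive rate depends entirely on its definition.

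**What to change.** 1. State in 8.1 and 13.2.5 that target lesions removed at surgery, identified from the operative and pathology reports already collected, are not scored as response. A partly removed lesion should be treated as removed, since surgery also reduces its diameter. Compute any RECIST response rate only in patients with at least one baseline target lesion left in place. Use only those lesions in both the baseline and the follow-up sums, and report how many such patients there are.
2. For the other patients, report recurrence or progression at 3, 6 and 12 months from the Follow-Up Form (Appendix F), by the resection status already on the Surgery Form (Appendix D).
3. Cite one RECIST version in 5.2.5, 8.1 and 13.2.5, with its lesion limit and response definitions, and align Appendix G with it.

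**Cost.** Wording changes, a small change to Appendix G, and staff time to match target lesions to the operative and pathology reports. No new scans or visits are needed. The rule uses baseline lesions left in place because lesion size after surgery is not measured before the 3-month CT. The response rate will be less favourable and will rest on few patients: if only 5 had a target lesion left and 1 responded (an assumed case), the rate would be 20% with an exact 95% confidence interval of 0.5% to 71.6%.

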8.3 Methods for Evaluation of Quality of Life

The principal parameters employed to assess the QOL and symptoms are the following self-administered questionnaires: FACT-O (FACT-G with 27 items plus 12 items specific to ovarian cancer). These questionnaires are to be completed at eight time points. The primary outcome will address FACT-O scores, but additional assessments of abdominal pain by FACT/GOG-AD and neurological symptoms by FACT/GOG-Ntx.

